Suicide prevention is a priority of the VHA with national leadership setting the goal of getting Veteran suicide to zero. This study is designed to: decrease suicide rates in Veterans during periods of increased risk (i.e., post-hospital discharge, following a suicidal crisis); add to our knowledge of how to maximize treatment benefits for Veterans with suicidality; discover whether combining TMS to an empirically-based therapy for suicide increases effectiveness compared to BCBT monotherapy; and collect neurocognitive data that will facilitate future optimization of treatment delivery and prescription. Despite the promise of both treatment modalities – TMS and BCBT – to our knowledge no one has prospectively studied the combination of these two interventions. Furthermore, few studies conducted in Veterans have examined brain-based biomarkers of suicidality and/or response to interventions for suicide. Collectively, our team has expertise in suicide, TMS, and neuroimaging, and are well-qualified to evaluate the effectiveness and biological mechanisms of a combined TMS+BCBT treatment for suicide.

A2. Primary Hypotheses:

- Compared to sham TMS+BCBT, Veterans receiving active TMS+BCBT will demonstrate greater reductions in suicidal behaviors.
- Suicide symptom reductions after TMS+BCBT will be correlated with changes in brain function in executive control regions.

A3. Secondary Hypotheses:

Compared to sham TMS+BCBT, Veterans who receive active TMS+BCBT will have:

- Reduced suicide attempts and/or longer time to first attempt.
- Superior improvements in psychosocial functioning.
- Reduced suicidal ideation severity.
- Fewer psychiatric hospitalizations/crisis visits during the follow-up period.

A4. Moderator and Mediator Effects:

In addition to these specific hypotheses, we will conduct:

- Exploratory latent growth curve analyses to compare the trajectory of change for primary, secondary, and tertiary outcomes (i.e. linear ascending, descending, or quadratic between sham TMS+BCBT versus active TMS+BCBT).
- We will include moderator variables in these models (e.g. diagnosis, comorbidity, gender), which may identify specific patient groups who will benefit from the addition of active TMS+BCBT versus sham TMS+BCBT.
- We will investigate mediating variables to determine the mechanisms through which TMS produces its effects on clinical outcomes.

A5. Exploratory Brain-Behavior Hypotheses

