- Brain and behavioral correlates of decision-making, impulsivity, and executive control at baseline will differ between Veterans with suicidality and non-suicidal Veteran controls.

- Improvement in suicide symptoms after treatment will be predicted by brain and behavioral correlates of decision-making and executive control at baseline.
- Improvements in suicidality will be associated with functional changes in decision-making circuits.
- Machine learning models predicting longitudinal outcomes that merge brain, cognitive, and electronic health record (EHR) data will outperform models based solely on EHR.

B. BACKGROUND

The tragedy of Veteran suicide cannot be overstated. Twenty Veterans die each day of suicide [1]. Suicide in female Veterans has increased substantially in the last 5 years [1]. Suicide attempt rates are also climbing. The Veterans' Health Suicide Prevention Application Network (SPAN) reported that over 900 suicide attempts per month occurred in 2014 - an unacceptable increase from 600 per month in prior reports [1]. The presence of a single episode of suicidal ideation or attempt places an individual at greatly increased future risk [2]. Research in civilian populations demonstrated that suicide attempters are 38 times more likely to die of suicide than those without history of attempts [3]. In the year following a suicide attempt, 0.8 – 2.6% of previous attempters died of suicide; mortality estimates 9 years post attempt are as high as 5-11%[4].

One estimate suggests that approximately 15% of all individuals with one or more suicide attempts will eventually die of suicide [5].

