BL** = If assessments are not completed at baseline visit, they may be completed at next research appointment (i.e., first MRI appointment)

I = Intervention - weekly (every 5 session) rating scales are assessed following standard PVAMC clinical neuromodulation treatment protocols

I^ = Assessment is given during the 12 weekly BCBT therapy visit

EP = 12th intervention therapy visit, 12 weeks (3 months) from start of intervention

F/U = 6-, 12-, and 24- month follow-up visits. Veterans will attend the follow-up visits per study involvement as described in *Section D4.1 Study Visits*.

F/U* = Measure is not administered in the absence of history of STBs

D4.2 MRI Visits and Cognitive Battery

All MRI visit activities (pre-intervention/post-intervention and for control participants) will involve the same procedures. Specifically, all will include self-reports, a brief battery of PhenX and NIH Toolbox cognitive test delivered via iPad, and an MRI scan. All visits will take place in a private consult room in PVAMC building 32 and the PVAMC MRI Suite.

MRI Visit 1 activities will occur as soon as scheduling allows after baseline visit, prior to the start of TMS+BCBT intervention, if applicable, and MRI Visit 2 will occur post-intervention, if applicable, as soon as scheduling allows following the final intervention appointment. Control participants will have the MRI visit as soon as scheduling allows following the baseline visit.

Cognitive testing data is collected with a laptop during some MRI scans. Images will be acquired on a Siemens (Erlangen, Germany) PRISMA 3T scanner and 64-channel head coil at the PVAMC MRI facility. All equipment used in the scanning room are MRI compatible. Participants will receive \$75 for completion of the MRI visit. Compensation will be prorated for participants who do not complete the MRI scan if an attempt to complete the MRI scan is made.

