We will conduct 1 interim analysis and assess our primary aim when we have enrolled 32 persons per treatment group (~50% enrollment). The analyst and investigators will be blinded to treatment assignment in the interim analysis. We will test our a priori hypotheses and suggest consideration of early stopping to the DSMB if either group shows an effect on the primary outcome using O'Brien-Fleming stopping bounds [45] (i.e., a significance level of 0.0054). We will retain a significance level of 0.049 for our primary hypothesis at project completion.

E2.2 Primary hypothesis

We hypothesize that compared to sham TMS+BCBT, Veterans receiving active TMS+BCBT will demonstrate superior improvements in suicidal ideation and fewer suicide attempts. Our primary outcome for this aim is a composite measure of suicide behavior based on occurrence of any of five types of suicidal behavior: death by suicide, suicide attempt, interrupted or aborted attempts, and suicide preparatory acts. This composite score is derived from the Columbia Suicide Severity Rating Scale (C-SSRS). The C-SSRS captures data on number of attempts, aborted attempts, and interrupted attempts. Number of suicide behaviors will be added across these categories to yield a total suicide events score. Death by suicide will be captured by review of medical records and death records. The main exposure variable of interest is the random treatment assignment. Our analytic approach will be an ANCOVA-type mixed effect regression model [72]. This means the outcome composite measure at follow-up time points (e.g., 3, 6, 12 months) will be regressed on baseline value of the outcome, design factors, and treatment assignment, dummy variables for time (baseline as reference) and interactions of treatment assignment and time dummies. Random intercepts and exchangeable error covariance structure will accommodate non-independence of observations owing to the repeated measures design.

The main effect of TMS as adjunctive to BCBT will be tested with the main effect of group assignment to the joint intervention condition. The time effect interactions of TMS assignment test hypotheses about the maintenance of gains at 3, 6 and 12 months. Our main hypothesis is that there is an immediate beneficial effect of TMS exposure. For our secondary outcome, (time to first suicide attempt over 12 months) we will use a Cox proportional hazards model analysis framework.

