E2.3.1 Statistical power and sample size considerations: Sample size considerations for part

(a) are similar to the primary hypothesis, and the minimum detectable effect size difference is a standardized mean difference of 0.5SD units. Without pilot data on the number of hospitalizations/crisis visits, it is difficult to forecast the distribution and detectable difference in distribution on the count outcome (part b). Rules of thumb provided by Van Belle [77] suggest we will be able to detect a relative rate of $\exp(4/\sqrt{n})$, where n is the per-group sample size, or a reduction in the rate of hospitalizations of about 61% or more among those receiving active TMS+BCBT plus versus sham.

E2.4 Moderator and mediator effects

In addition to the above hypotheses, we will conduct exploratory latent growth curve analyses to compare the trajectory of change for primary, secondary, and tertiary outcomes (i.e. linear ascending, descending, or quadratic) between sham TMS+BCBT versus active TMS+BCBT. We will include moderator variables in these models (e.g. diagnosis, comorbidity, gender), which may identify patients who will benefit more or less to the addition of active TMS+BCBT versus sham TMS+BCBT. We also will investigate mediating variables to determine the mechanisms through which TMS produces its effects on clinical outcomes. The set of analyses in this aim are motivated by [78], who suggest exploratory, hypothesis generating analyses be conducted after primary study aims are addressed to attempt to decide for which sample sub-groups the intervention might be more efficacious or have more lasting effects. The analytic approach will be like that described for the primary and secondary aims, although in addition to the timepoint effect indicators, we will examine models with more parsimonious time structure (e.g., linear, piecewise linear, negative exponential) and then attempt to describe factors that predict variations in important components of the implied change trajectory. We will make use of generalized linear mixed effect models and compare alternative time bases using information criteria before adding covariates, mediators, and moderators. Treatment effect mediation will be evaluated by comparing treatment effects estimated before and after adjusting for the main effect of putative mediators. Moderation effects will be examined as three-way interactions of the putative moderator, treatment assignment, and time.

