E2.4.1 Statistical power and sample size considerations: As we view tertiary analyses as exploratory and hypothesis generating, we do not present a priori specified sample size or minimum detectable effect size statistics. We have no doubt that we may be underpowered to detect all but large moderation effects. Our inferences will be made cautiously and be guided

by confidence intervals obtained by bootstrap resampling of the observed data.

E3. Aim 2 Analytical Plan (Analyses Related to Cognition and Neuroimaging)

All de-identified data from this study for Aim 2 will be combined with data from subjects who completed neuroimaging procedures in PVAMC IRB protocol #2018-051.

E3.1 Evaluate the relationship between STBs and reward circuits involved in decision-making in Veterans.

Hypothesis: Neural and behavioral correlates of decision-making will differentiate Veterans with STBs from those without STBs.

Rationale: Suicidality is associated with maladaptive decision-making. Neuroimaging in non-Veterans has shown that STBs are accompanied by functional and anatomical differences in the striatal-to-VMPFC reward circuit implicated in decision-making. It is unknown if these potential neurocognitive markers of suicide generalize to Veterans.

Between-group contrasts of decision-making, structural MRI, and functional MRI will be used to test our hypothesis.

E5.1 Participant groups: The STB group will be comprised of Veterans hospitalized for suicide attempt (up to n=30) or suicidal ideation (up to n=30). The diagnosis matched control group is comprised of Veterans (up to n=60) without current STBs. Per power estimations computed with G Power software⁴², 85% power to detect a medium-sized effect of group (0.4) in an ANCOVA model with three groups and two covariates is afforded by a total sample size of 72, or n=24 participants per group. Our enrollment targets exceed this estimate to account for loss of participants that are unable to complete all aspects of the study.

Data sources: Decision-making tasks include the scanned reward expectancy task (card guessing), and the un-scanned Iowa Gambling and Monetary Choice (Delay Discounting) tasks. Structural MRI and diffusion MRI data. FMRI data used in Aim 1 analyses will come from either the card guessing reward task or resting state functional MRI runs.

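### The second Primary Hypothesis (symptom reduction correlates with change in executive-control brain function) is assigned to no analysis in Section E

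*Combined protocol and SAP*

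**What the plan says.** - **Hypotheses.** A2 has two Primary Hypotheses. The first concerns suicidal behaviors by arm. The second is "Suicide symptom reductions after TMS+BCBT will be correlated with changes in brain function in executive control regions". A5 adds exploratory hypotheses on treatment response: that baseline brain and behavioral measures predict improvement, and that "Improvements in suicidality will be associated with functional changes in decision-making circuits".
- **Data collection.** D4.2 gives both MRI visits the same procedures and states that "MRI Visit 2 will occur post-intervention, if applicable, as soon as scheduling allows following the final intervention appointment".
- **Treatment analyses.** E2.2, the only analysis section headed as the primary hypothesis, says: "Our primary outcome for this aim is a composite measure of suicide behavior based on occurrence of any of five types of suicidal behavior". E2.1 uses the singular: "We will retain a significance level of 0.049 for our primary hypothesis at project completion". E2.3 covers disability score, hospitalizations or crisis visits, and ideation. In E2.4, "We also will investigate mediating variables to determine the mechanisms through which TMS produces its effects on clinical outcomes".
- **Imaging analyses.** E3.1 says: "Between-group contrasts of decision-making, structural MRI, and functional MRI will be used to test our hypothesis". E3.2 compares attempters, ideators and controls in cognitive control regions, and also regresses decision-making measures on activation and connectivity. E3.3 classifies suicidal history from health-record and task data. E3.4 is preprocessing.
- **Imaging sample and power.** E1 gives a biomarker subsample of 30 ideators, 30 attempters and 60 controls. The E3.1 participant-group paragraph claims 85% power for a group effect of 0.4 with 72 participants in three groups and two covariates.

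**The concern.** A primary hypothesis should have a named outcome, predictor, model, alpha and sample-size statement. This one has none of them, although the protocol asks intervention participants who are scanned to return for a second two-hour visit.

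If nothing is added, the hypothesis is either not tested or is tested by an analysis chosen after the data are seen. The room for choice can be counted from the protocol. E3.2 names six prefrontal and cingulate regions (three ventrolateral, one dorsolateral, two cingulate). Table 4 lists three fMRI paradigms (resting, reward, stop-signal). At least three symptom measures are candidates: C-SSRS ideation, the Beck Scale for Suicide Ideation, and the IDS-SR suicide item used in the pilot work in C3. That is 6 × 3 × 3 = 54 versions before choosing between activation and connectivity, or between pooled arms and an interaction. The Bonferroni rule in E3.2 covers only the choice of region.

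**Working it through.** **1. Search of Section E.** The hypothesis needs a brain-change variable and a symptom-change variable in one model.

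| Section | Outcome or contrast | Uses MRI 2 or brain change? | Uses symptom change or arm with a brain measure? |
|---|---|---|---|
| E2.2 | Suicidal behavior composite by arm | No | No brain measure |
| E2.3 | Disability, hospitalizations/crisis visits, ideation by arm | No | No brain measure |
| E2.4 | Trajectories, moderators, mediators | None named | None named |
| E3.1 | Suicidal v non-suicidal, reward circuit | None named | No |
| E3.2 | Attempt v ideation v control; regressions of decision-making | None named | No |
| E3.3 | Classification of suicidal history | None named | No |
| E3.4 | Preprocessing | Not an analysis | No |

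E3.2 uses the right regions, but not for change.

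**2. The plan's own imaging power figure.** Inputs from E3.1: effect f = 0.4, three groups, two covariates, N = 72; alpha .05. With df1 = 2, df2 = 72 − 3 − 2 = 67 and noncentrality 0.4² × 72 = 11.52, the noncentral F gives power 85.3%. At N = 71 it is 84.8%, so 72 is the smallest N that reaches 85%. The figure reproduces, but it describes a cross-sectional group effect and says nothing about a correlation of changes.

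**3. How many scan pairs?** The documents do not say. Three illustrative values:
- 60: all 30 + 30 suicidal Veterans in the E1 subsample, with no loss.
- 48: the same with an assumed 20% loss (0.8 × 60).
- 104: 130 randomized less the roughly 20% with an MRI contraindication expected in D2.2 (0.8 × 130), assuming that all others are scanned twice.

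**4. Detectable partial correlation.** For a model adjusting for k = 4 covariates (baseline score, arm, age, sex), the Fisher approximation is

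r = tanh[(z(1−α/2) + z(0.80)) / √(n − 3 − k)].

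For one test at .05 the numerator is 1.960 + 0.842 = 2.802. With Bonferroni over six regions, α = .05/6 = .00833 and the numerator is 2.638 + 0.842 = 3.480.

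| Pairs n | √(n − 7) | r, one test | r, six regions |
|---|---|---|---|
| 48 | 6.403 | 0.41 | 0.50 |
| 60 | 7.280 | 0.37 | 0.44 |
| 104 | 9.849 | 0.28 | 0.34 |

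E3.2 also tests striatal regions; counting those would raise the right-hand column.

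**The case against.** The best counter-argument is E2.4, which promises mediator analyses of how TMS works; a brain-change mediator could be entered there. But the section is exploratory, names no imaging variable or visit, and judges mediation by comparing treatment effects before and after adjustment. That is not a test of whether symptom change and brain change are correlated. It softens the gap without closing it.

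A second argument is that E2.1 and E2.2 treat the primary hypothesis as singular and attach the final alpha to the behavioral outcome, so the imaging hypothesis may never have been meant as confirmatory. That is plausible, but A2 then carries the wrong label.

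A reader might also infer more than the text supports:
- **That the second scan is never used.** The E3 data-source paragraphs do not say which visit they draw on, and the preprocessing would apply to any scan. What can be said is that no analysis names it.
- **That at most 60 Veterans will have both scans.** The 30 + 30 is the size of the biomarker subsample, not a cap on MRI 2. The number could be higher, since 130 are randomized. It could be lower, since D4.5 allows Veterans to take part in imaging only, and they have no post-intervention scan.
- **That all imaging analyses are group contrasts.** E3.2 includes regressions as well, though these too are cross-sectional.
- **That the trial cannot answer the question.** The scans are scheduled; what is missing is the prespecified analysis.

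**Conclusion.** The point stands. A stated Primary Hypothesis has no assigned analysis, alpha or sample-size statement in Section E, and the two A5 hypotheses on treatment response share the gap. This is more than missing detail, because the plan could be followed exactly and the hypothesis would remain untested.

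The consequence is limited to the imaging aim. The comparison of active and sham TMS on suicidal behavior, and its alpha of 0.049, are unaffected.

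The detectable partial correlation runs from about 0.28 (104 pairs) to 0.41 (48 pairs) for a single test, and from 0.34 to 0.50 across six regions. These figures rest on assumed numbers of pairs, 80% power, two-sided .05 and four covariates. They show what a prespecified test could detect; they are not evidence that such an effect exists.

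**What to change.** Add an E3 subsection for the A2 brain-change hypothesis.

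- **Outcome:** C-SSRS ideation severity at endpoint. Table 2 collects the C-SSRS at baseline and endpoint.
- **Model:** regress it on baseline severity, MRI 2 minus MRI 1 change in one named region and measure, arm, age and sex. Test the change coefficient.
- **Region and measure:** name one. A candidate that E3.2 already defines is ventrolateral prefrontal activation on successful stop trials of the stop-signal task. Say which of its three subregions is used, or fix an average of them in advance.
- **Other tests:** treat the arm-by-change interaction as exploratory. Apply the existing Bonferroni rule to each remaining E3.2 region.
- **Alpha:** state the level and how it relates to the 0.049 kept for the behavioral outcome.
- **Missing scans:** say how absent MRI 2 data are handled, and whether the multiple imputation in E1.1 extends to them.
- **Sample size:** give the expected number of scan pairs, or a range, with the detectable partial correlation.

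Assign analyses to the two A5 treatment-response hypotheses in the same place. If the sponsor does not want a confirmatory test, relabel the hypothesis in A2 as exploratory.

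Either route is a text change, with no added visits, participants or procedures. It should be made before the change data are examined. The one drawback is that sensitivity will be seen to be modest: with 60 pairs or fewer, a single test reaches 80% power only for correlations of about 0.37 or more.

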Design considerations & alternative strategies for Aim 2. This design uses a categorical factor to define groups that approximates risk by history of attempt versus ideation, based on the strength of previous attempt as a risk factor for subsequent attempts. While straight-forward, we acknowledge that within-group heterogeneity may invalidate this grouping strategy. For instance, the ideation group could contain a significant number of Veterans with highly detailed suicide plans that have begun obtaining means that would be better classified as high-risk. In recognition of this issue, we will also compute empirically-determined risk categorization thresholds based on Beck Lethality Scale, Suicide Intent Scale, and Scale for Suicide Ideation scores. Alternatively, we may use continuous variables operationalizing suicidal planning, intent, or lethality for these analyses.

E3.3 (Exploratory) Integrate EHR data and neurocognitive markers into predictive models of STBs.

We will combine EHR data and objective cognitive measures forming a high-dimensional, multi-modal dataset. Machine learning algorithms will be applied to examine the predictive utility of this approach.

Rationale: Machine learning algorithms can accommodate large predictor sets and can model complex interactions among factors. Models built on EHR outperform traditional models with predictive accuracy in excess of AUC +0.70. We will subject an EHR dataset enriched with additional, objective, cognitive measures of suicidality (defined in Aims 1 & 2) to machine learning classification. Three types of supervised machine learning models (described below) will be used for this exploratory analysis. Models will be constructed both with, and without, Aim 1 & 2 measures to test if their inclusion improves suicide prediction.

Data sources: Aggregated EHR data (Section D6.2) and subject-level performance outcomes on the reward expectancy scanned task, Delay Discounting task, Iowa Gambling Task, Flanker Task, Dimensional Card Sort Task, and SSRT task.

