General approach: The dataset comprised of subject-level aggregated EHR variables and behavioral outcomes from cognitive control and reward tasks will be treated as a “discovery data set,” meaning that it will be used to train machine-learning algorithms and make initial identifications of subsets of the dataset associated with distinct suicide outcomes. Classifier training, cross-validation, and optimization will be performed using this discovery data set. The goal is to predict participants with: 1) history of attempt, 2) suicidal ideation without history of attempt, 3) no history of STBs. Future studies will attempt to replicate findings in an independent sample.

Software: Part of this exploratory aim involves testing implementations against one another. Modeling will be carried out using Julia⁶⁴, an open-source computing language, MATLAB, and R.

Machine learning algorithms:

Elastic Net Regularized Logistic Regression⁶⁵ Unlike other regularized regression methods such as ridge or lasso, elastic net models are stable when multicollinearity amongst

predictors is high. Elastic net regularization penalizes model complexity by specifically modeling overfitting simultaneously combining the shrinkage and recovery approaches of lasso and ridge regularization. This means that coefficients are all retained but undergo shrinkage toward zero. We will use a 10-fold cross-validation to assess the performance of the classifier.

Random forest machine clustering Random forest clustering is a tree-based supervised learning algorithm that can handle high multi-collinearity and is robust to overfitting [95]. Decision trees are built by recursively subsampling predictors from the training dataset [95,96]. At each “split” of a tree, the algorithm searches for a given variable and the binary decision that splits the predictor subset. As trees are built, progressively smaller predictor subsamples are drawn and used to predict earlier data splits forming “parent” and “child” nodes. The number of predictors at each node will be determined by the square root of the total number of predictors to limit over-fitting [96] and an error minimization criterion will be applied to select the predictor and cut point at each node of the decision tree that optimizes binary splits. This iterative process will continue down the tree until node size is equal to 10% of the total study sample. A 10-fold cross-validation will also be run as a preliminary validation of estimates.

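### A5's machine-learning hypothesis concerns longitudinal outcomes, but E3.3 only classifies existing suicide history and leaves unclear whether imaging is an input

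*Combined protocol and SAP*

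**What the plan says.** The fourth exploratory hypothesis in section A5 reads: "Machine learning models predicting longitudinal outcomes that merge brain, cognitive, and electronic health record (EHR) data will outperform models based solely on EHR".

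Section E3.3, itself labelled exploratory, is the only part of section E that describes machine learning. Its main elements are:

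- **Target.** "The goal is to predict participants with: 1) history of attempt, 2) suicidal ideation without history of attempt, 3) no history of STBs".
- **Inputs.** Aggregated EHR data and "subject-level performance outcomes on the reward expectancy scanned task, Delay Discounting task, Iowa Gambling Task, Flanker Task, Dimensional Card Sort Task, and SSRT task". The paragraph on general approach describes the training data in the same way: "The dataset comprised of subject-level aggregated EHR variables and behavioral outcomes from cognitive control and reward tasks".
- **Comparison.** "Models will be constructed both with, and without, Aim 1 & 2 measures to test if their inclusion improves suicide prediction".
- **Metric.** Area under the ROC curve (AUC), with the highest value taken as best.

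The wording that bears on imaging points both ways. The heading is "Integrate EHR data and neurocognitive markers into predictive models of STBs", which could take in brain measures. The opening sentence is narrower: "We will combine EHR data and objective cognitive measures forming a high-dimensional, multi-modal dataset". The rationale describes the added inputs as "additional, objective, cognitive measures of suicidality (defined in Aims 1 & 2", which again says cognitive.

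Follow-up data exist. Table 2 schedules the C-SSRS at endpoint and at the 6, 12 and 24-month visits. It schedules the SSI at follow-up too, except for participants with no history of suicidal thoughts and behaviours (STBs). Section D5 extracts EHR data at baseline, six months, one year and two years. E3.3 names none of these as an outcome.

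**The concern.** A model that sorts Veterans by what has already happened answers a different question from one that says what will happen next. A high AUC for the former is not evidence for the latter. Section B5.3 motivates this work as better risk modelling for prevention, and E3.3 itself speaks of suicide prediction. A reader who starts from A5 would therefore naturally take the E3.3 AUCs as the answer to the longitudinal hypothesis.

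The inputs raise a second problem. If imaging features are left out, neither a gain nor a lack of gain over the EHR model says anything about brain measures. If they are let in under the general reference to Aim 1 and 2 measures, the plan does not say which ones, and the choice is made during analysis.

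The history target also sits close to its own predictors. Table 5 lists suicidality, current and lifetime, among the EHR variables, so the EHR-only comparator may already hold a chart record of the label.

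At stake are the meaning of one exploratory result and the use made of follow-up data that the trial already collects.

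**Working it through.** The plan gives no sample size, power or alpha for E3.3, so there is no figure to reproduce. The check sets the hypothesis against the analysis.

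**Step 1. Element by element.**

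| Element of the A5 hypothesis | In E3.3? |
|---|---|
| Longitudinal outcome | No. Three classes of existing history; no follow-up outcome, horizon or window |
| Brain predictors | Unclear. Absent from both explicit input lists; two looser phrases could cover them |
| Cognitive predictors | Yes. Performance on six tasks |
| EHR predictors | Yes |
| Comparison with EHR-only models | Yes. Models with and without the added measures, ranked by AUC, with no interval or test for the difference |

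Three elements match, one is missing and one is ambiguous.

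**Step 2. Does another section supply the missing analysis?** E2.4 covers treatment trajectories, moderators and mediators. E3.1 and E3.2 are group contrasts and associations. None of them is a predictive model of follow-up outcomes compared with an EHR-only model.

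**Step 3. Imaging inputs.** E3.1 and E3.2 define morphometry, tractography, fMRI activation and connectivity measures, so a reference to Aim 1 and 2 measures could include them. E3.3, however, calls those measures cognitive, and its data-source list names only performance on the tasks. Two of the six tasks are done in the scanner, but it is performance on them that is entered.

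**Step 4. What a prospective target could bear.** This is illustrative only.

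- Inputs: 30 + 30 = 60 Veterans with suicidality in the biomarker subsample (E1), and 12-month attempt risks of 21% and 4.5% (E2.2.1).
- Formula: expected number with an attempt = n × risk.
- At 21% throughout: 60 × 0.21 = 12.6.
- Split evenly between arms, reading 21% as the sham risk: 60 × (0.21 + 0.045)/2 = 60 × 0.1275 = 7.65.

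That is roughly 8 to 13 Veterans. The range assumes the full 60, although E3.1 and E3.2 give each group of 30 as a ceiling. It applies no attrition. The even split also assumes that all 60 are randomised, whereas the section on follow-up visits allows imaging-only participants. Pooling with protocol #2018-051 (E3) could change the number analysed. The mismatch in Step 1 does not depend on these counts. They show only that a binary event should not carry a prospective analysis alone, and that a severity score is the better lead target.

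**The case against.** The strongest defence is that this aim is openly exploratory. E3.3 treats its data as a discovery set, leaves replication to future studies and concedes that the sample is small. It does plan the comparison with EHR-only models, so a narrower form of the hypothesis is tested. All of that stands, and it limits the weight of the point. It does not make a history label a longitudinal outcome, and the limitations listed in E3.3 do not mention the target.

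Four stronger readings are tempting, and the documents do not support them.

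- *Imaging is excluded.* A reader might infer this from the input lists, but the heading and the reference to Aim 1 and 2 measures leave it open. The supportable statement is that E3.3 is unclear.
- *The classification is made at baseline.* E3.3 gives no index time, and EHR data are also extracted at follow-up. What is certain is that the classes describe existing history.
- *The classifier merely recovers the recruitment group.* Recruitment under D2.1 rests on a current episode within 2 weeks, and controls need only lack current suicidality. The E3.3 classes are defined by history. A control, or a Veteran recruited for ideation, may have a past attempt, so class and recruitment group can differ.
- *The expected number of events is known.* The range in the working rests on ceilings and planning rates, and is an illustration.

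**Conclusion.** The point holds in limited form. A5's fourth hypothesis and E3.3 disagree on the outcome, and E3.3 is ambiguous on whether brain measures enter. Carried out exactly as written, E3.3 shows whether cognitive measures improve classification of suicide history over EHR data alone. Its result, in either direction, could not support or refute the longitudinal claim.

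This rests on the text of A5 and E3.3 and on no other section supplying the analysis; it needs no numerical assumption. The consequence is confined to an exploratory aim. The randomised comparison, the primary outcome and the interim analysis are unaffected. The plan should be corrected because the correction is cheap and the data are already scheduled.

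**What to change.** Either of two changes resolves the mismatch.

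**Option 1: make E3.3 test the hypothesis.**

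- Add a prospective target with a stated window: C-SSRS ideation severity at 6 and 12 months, and the SSI among Veterans with STB history, since it is not given to others at follow-up. Make any C-SSRS suicidal behaviour by 12 months a secondary target, because few events are expected.
- Use only predictors measured before the intervention starts, or at the baseline and first MRI visits for Veterans who are not treated. Take EHR predictors from the baseline extraction only; each later extraction looks back 12 months and would overlap the outcome window.
- Name the imaging inputs: the region-of-interest measures of both E3.1 and E3.2.
- Account for randomised arm among treated Veterans, for example by entering it in every model compared.
- State whether matched controls are in the analysis set. If they are, part of any accuracy will come from separating them from Veterans enrolled with suicidality.
- Compare cross-validated performance with and without the brain and cognitive measures, and give an interval for the difference. A severity score needs an error or explained-variance measure in place of AUC.
- Keep the three-class model as an explicitly cross-sectional analysis, and say whether Table 5's suicidality item stays among its EHR inputs.

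**Option 2: reword A5.** Describe the fourth hypothesis as cross-sectional classification of suicide history from EHR and cognitive data, and align the reference to suicide prediction in E3.3.

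Both options change text only and need no new data. Option 1 costs some extra exploratory analysis of limited precision. Option 2 costs nothing further but gives up the longitudinal question.
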